Partial prevalence	In partial prevalence outcome events are considered to persist for a fixed amount of time following an initial diagnosis. That is, to be a prevalent case at a given time, an individual must have had the outcome observed for the first time during a fixed time in the past (e.g. 5 years).

	D2.2.3 – Study Protocol for C1-001	
	Author(s): [name], [name], [name], [name]	Version: 2.0 - Final
	Dissemination level: Public	

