8. RESEARCH METHODS

8.1 Study type and Study Design

Population-level descriptive epidemiology within a cohort study. Study design diagrams with description of follow-up are described below. The study will include all people in a database and, for the primary analysis, have a year of prior history available. The prevalence of each outcome of interest calculated on an annual basis as of the 1st January for each year, estimated overall and stratified by age and sex. As a sensitivity analysis annual period prevalence will also be estimated. 5-year partial prevalence will be used for the primary analysis, with individuals will be considered as a prevalent case if they have had their first diagnosis in the prior 5 years. In sensitivity analyses, 2-year partial prevalence and complete prevalence will be estimated. For the latter, once identified as a case, an individual will remain so until their exit from the study.

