8.6.2. Outcome/s (where relevant)

Outcome cohort definitions for partial and complete prevalence

Complete prevalence represents the number of persons alive at the specific point in time regardless of how long ago the diagnosis was, while partial prevalence limits the number of patients to those diagnosed during a fixed time in the past.⁶ To operationalise this definition outcome cohorts will be defined which vary in how the cohort exit is defined. For complete prevalence an individual will remain in the outcome cohort until the end of their observed time at risk. Meanwhile, for partial prevalence, an individual will exit the outcome cohort after a certain number of days has elapsed since the first record indicating them to be a prevalent case (e.g. 1,825 days for 5-year partial prevalence).

Follicular lymphoma

Follicular lymphomas are the second leading Non-Hodgkin’s lymphomas and can be diagnosed accurately on morphologic findings alone: B-cell in follicular centre. Many patients are diagnosed incidentally or at a time when their lymphoma is not causing symptoms or signs of organ function impairment. The major differential diagnosis is between lymphoma and reactive follicular hyperplasia. The coexistence of diffuse large B-cell lymphoma must be considered. Patients with follicular lymphomas are often subclassified, or graded, into those with predominantly small cells, those with a mixture of small and large cells, and those with predominantly large cells. The typical natural history is a pattern of continuous relapses with a diminishing sensitivity to chemotherapy. On average, most patients will live with follicular lymphoma for 15 to 20 years.

For this study, cases will be identified based on a record indicating a diagnosis or observation of follicular lymphoma. A clinical description along with a preliminary code list is provided in Appendix 1. For the primary analysis, 5-year partial prevalence will be estimated and so individuals will be considered as a prevalent case if they had a relevant record observed in the prior 1,825 days. In sensitivity analyses, 2-year partial prevalence

	D2.2.3 – Study Protocol for C1-001	
	Author(s): [name], [name], [name], [name]	Version: 2.0 - Final
		Dissemination level: Public

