8.8 Analysis

Prevalence summarises the total number of individuals who have the outcome of interest at a particular time or during a particular period divided by the population at risk of having the outcome at that time or during the period. Point prevalence gives the proportion of individuals in a population who have the outcome at a given point in time, while period prevalence gives the proportion of individuals with the outcome at any time during a specified time period or interval. A key aspect here is that an outcome is defined in the sense of having a duration, with a start and an end date. As mentioned above, in partial prevalence the outcome end date is determined by a fixed number of days since the first record of the outcome event whereas in complete prevalence the outcome end date is defined as the end of observation time for an individual who has at some point prior had a record of the outcome.

For an example of calculations of point and period prevalence under partial prevalence see **Figure 3** below. It can be seen that at time $t+2$, two of the five study participants are in an outcome cohort giving a point prevalence of 40%. Period prevalence between $t+2$ and $t+3$ in this simple example would give the same answer. However, for the period t to $t+1$ the result will depend on whether study participants are required to have been observed for the full study period. If no such restriction is imposed all five study participants would contribute, but if study participants had to have been observable for the full period, then only three of the study participants would contribute.

In this study the primary analysis will use point prevalence, estimated as of the 1st January of each calendar year. We will also estimate period prevalence as a sensitivity analysis, estimated on an annual basis (between the 1st January and 31st December for each year). Period prevalence will first be estimated with participants required to contribute a minimum of only one day of the period to be included. Subsequently, we will estimate period prevalence with participants required to be observed for the full period for them to be included.

	D2.2.3 – Study Protocol for C1-001	
	Author(s): [name], [name], [name], [name]	Version: 2.0 - Final
	Dissemination level: Public	

[figure not shown]

Figure 3. Point and period prevalence

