23	Sensitivity	Period prevalence (annual)	0 days	Full year
24	Sensitivity	Point prevalence	1095 days	N/A
25	Sensitivity	Period prevalence (annual)	1095 days	One day
26	Sensitivity	Period prevalence (annual)	1095 days	Full year

*For 5-year partial prevalence individuals will be considered as a prevalent case if they had their initial diagnosis observed in the prior 1,825 days. *For 2-year partial prevalence will be considered as a prevalent case if they had a relevant record observed in the prior 730 days. †For complete prevalence individuals will be considered as a prevalent case if they have ever had a relevant record previously.

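### The 5-year case sentence in section 8.6.2 (all six cancers) and the 2-year footnote of Table 5 drop the first-record condition that the rest of the protocol applies to partial prevalence

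*Protocol*

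**What the plan says.** Most of the protocol defines a partial-prevalence case by the first record:

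- Glossary, partial prevalence: "an individual must have had the outcome observed for the first time during a fixed time in the past".
- Section 8.1, with the same rule in the abstract: "individuals will be considered as a prevalent case if they have had their first diagnosis in the prior 5 years".
- Section 8.6.2, opening paragraph on outcome cohorts: a person leaves the cohort after "a certain number of days has elapsed since the first record indicating them to be a prevalent case".
- Section 8.8: "in partial prevalence the outcome end date is determined by a fixed number of days since the first record of the outcome event".
- Table 5, 5-year footnote: "individuals will be considered as a prevalent case if they had their initial diagnosis observed in the prior 1,825 days".

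Two places leave the condition out:

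- Section 8.6.2, in the paragraph for each of the six cancers: "individuals will be considered as a prevalent case if they had a relevant record observed in the prior 1,825 days". The same paragraphs describe the 2-year analysis as using records from the previous 730 days, again without restricting to the first.
- Table 5, 2-year footnote: people "will be considered as a prevalent case if they had a relevant record observed in the prior 730 days".

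**The concern.** The two rules select different people. Someone diagnosed 8 years ago whose cancer was coded again last year has a record inside the 1,825-day window, but not a first record. That person counts under the cancer-specific sentences of 8.6.2 and does not count under the glossary, 8.1 or 8.8.

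Repeat coding is to be expected. The preliminary code lists for multiple myeloma, chronic lymphocytic leukaemia, acute myeloid leukaemia and acute lymphocytic leukaemia include remission and relapse codes, and the first three also include a history code. The two lymphoma lists have no such codes, so there a repeated diagnosis code would have the same effect.

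The conflict reaches the primary analysis of all six objectives. Read literally, the adjacent 5-year and 2-year footnotes of Table 5 also give the primary analysis and its sensitivity analysis different case rules. The results are meant to be read against the orphan threshold of 5 in 10,000 and over time (section 6), and five data partners will run one shared program, so the case rule needs a single meaning.

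**Working it through.** The protocol states no ratio between the two rules and no expected prevalence, so there is no plan figure to reproduce. The question is how far apart the two counts could be.

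**Inputs from the protocol.** Follicular lymphoma survival 15 to 20 years (8.6.2). Acute myeloid leukaemia: about 1 in 4 alive at 5 years (8.6.2). Multiple myeloma: median survival 30 to 60 months (Appendix I). IPCI: median follow-up 2.6 years. SIDIAP: data from 2006, mean follow-up 10 years (8.2). Threshold: 5 in 10,000 (section 6).

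**Quantity.** Ratio = (living cases with any record in the prior 5 years) / (living cases with first record in the prior 5 years), with constant incidence.

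**1. Idealised case for follicular lymphoma.** Everyone survives D years, every living case is re-recorded within 5 years, and the true first record is always visible. Ratio = D/5: 15/5 = 3.0 and 20/5 = 4.0. With exponential survival of mean D, the ratio is 1/(1 − exp(−5/D)): 3.5 and 4.5. Reading 15 to 20 years as a median instead gives 4.8 and 6.3.

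**2. Incomplete re-recording, full look-back.** With annual re-recording probability r, q = 1 − (1 − r)^5 and ratio = (5 + (D − 5)q)/5.

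| r | q | D = 15 | D = 20 |
|---|---|---|---|
| 0.1 | 0.410 | 1.8 | 2.2 |
| 0.2 | 0.672 | 2.3 | 3.0 |
| 0.5 | 0.969 | 2.9 | 3.9 |

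The protocol gives no re-recording frequency, so r is an assumption.

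**3. Limited look-back, complete re-recording.** For a person with 5 years or less of visible records, the first visible record must lie in the window, so the rules agree. If a share f has more than 5 years, ratio = D/(5f + D(1 − f)). Stated follow-up is taken as look-back, with an assumed exponential shape.

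- SIDIAP: f = exp(−5/10) = 0.607. D = 15: 15/(3.03 + 5.90) = 1.68. D = 20: 20/(3.03 + 7.87) = 1.83.
- IPCI: f = 0.5^(5/2.6) = 0.264. D = 15: 15/(1.32 + 11.04) = 1.21. D = 20: 20/(1.32 + 14.72) = 1.25. IPCI keeps history from before the observation period; if that history dates the first record, the ratio is higher.

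**4. Calendar limit.** From 1 January 2006 to 1 January 2010 is 1,461 days, less than 1,825. If SIDIAP holds no earlier records, the two rules give the same count on the first index date (ratio 1). On 1 January 2011 the span is 1,826 days, so they differ little if at all. They can separate only later.

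**5. Shorter-survival cancers, idealised as in step 1 with exponential survival.** Ratio = 1/(1 − S(5)). Acute myeloid leukaemia: 1/(1 − 0.25) = 1.33. Multiple myeloma: S(5) = 0.5^(5/2.5) = 0.25 gives 1.33, and S(5) = 0.5^(5/5) = 0.5 gives 2.0.

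**6. Against the threshold.** An inflation factor k moves a first-record prevalence across 5 in 10,000 if it lies between 5/k and 5. For k = 1.8 that is 2.8 to 5 per 10,000; for k = 1.2 it is 4.2 to 5.

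**The case against.** The strongest reply is that the protocol already settles the matter. The opening paragraph of 8.6.2 sets out how the outcome cohorts are built and fixes exit by days since the first record. Section 8.8 repeats that rule as something already stated, and the 5-year footnote of Table 5, which governs the primary analysis, agrees. The disputed sentence follows from the statement that 5-year partial prevalence will be estimated, so it reads as a loose paraphrase copied six times.

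Most of this stands. A reader might infer that 8.6.2 as a whole adopts an any-record estimand. The text does not support that, because its own cohort rule is first-record. What remains is that the cancer-specific sentences, taken as written, give a different rule. The same paragraphs do specify the first observed diagnosis for complete prevalence, so a programmer could take its absence for partial prevalence as deliberate. Table 4, with wash-out not applicable throughout, does not resolve it.

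A reader might also take 3- to 4-fold as the expected gap. It needs steady state, complete re-recording and full look-back together, and the follow-up stated for IPCI and SIDIAP points to much less.

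Nor would the any-record reading remove the contrast between the 2-year, 5-year and complete analyses. One coded contact per 5 years makes the 5-year count equal complete prevalence, but does not make the 2-year count equal either. The contrast shrinks.

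**Conclusion.** The protocol contradicts itself on the primary case definition. First record is the dominant and evidently intended rule; the six cancer paragraphs of 8.6.2 and the 2-year footnote of Table 5 are wrong as written.

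If the loose wording were programmed, the follicular lymphoma estimate would be inflated by a factor between 1 and an idealised 3 to 4 (fixed 15 to 20 year survival; higher still if survival is exponential). Under the stated follow-up the factor is about 1.2 in IPCI and 1.7 to 1.8 in SIDIAP. Those two figures rest on constant incidence, fixed survival, complete re-recording and an exponential look-back, the last three being assumptions about data the protocol does not describe. The protocol states no follow-up length for the other three databases, so none was calculated.

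The factor differs between databases and, in SIDIAP, can grow from 1 as look-back accumulates. It could therefore appear as a time trend or a country difference, and could change the reading against 5 in 10,000 for a cancer near the threshold.

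**What to change.** In all six cancer paragraphs of 8.6.2, define a 5-year case as a person who had *their first record of the cancer observed in the prior 1,825 days*. Change the 730-day phrases in those paragraphs and the 2-year footnote of Table 5 in the same way. This matches the cohort-exit rule already given in the opening of 8.6.2 and in 8.8, so the outcome cohort is coded as first record plus a fixed exit, and later records do not restart the window.

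The cost is wording in six paragraphs and one footnote, with no extra data or analysis. The milestones in section 5 still list creation of the analytical code as to be confirmed, so on the protocol's own timetable the change can be made before programming.

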8.7 Study size

No sample size has been calculated as this is a Disease Epidemiology Study where we are interested in the prevalence of haematological cancers in the entire population.

8.8 Analysis

Prevalence summarises the total number of individuals who have the outcome of interest at a particular time or during a particular period divided by the population at risk of having the outcome at that time or during the period. Point prevalence gives the proportion of individuals in a population who have the outcome at a given point in time, while period prevalence gives the proportion of individuals with the outcome at any time during a specified time period or interval. A key aspect here is that an outcome is defined in the sense of having a duration, with a start and an end date. As mentioned above, in partial prevalence the outcome end date is determined by a fixed number of days since the first record of the outcome event whereas in complete prevalence the outcome end date is defined as the end of observation time for an individual who has at some point prior had a record of the outcome.

For an example of calculations of point and period prevalence under partial prevalence see **Figure 3** below. It can be seen that at time $t+2$, two of the five study participants are in an outcome cohort giving a point prevalence of 40%. Period prevalence between $t+2$ and $t+3$ in this simple example would give the same answer. However, for the period t to $t+1$ the result will depend on whether study participants are required to have been observed for the full study period. If no such restriction is imposed all five study participants would contribute, but if study participants had to have been observable for the full period, then only three of the study participants would contribute.

In this study the primary analysis will use point prevalence, estimated as of the 1st January of each calendar year. We will also estimate period prevalence as a sensitivity analysis, estimated on an annual basis (between the 1st January and 31st December for each year). Period prevalence will first be estimated with participants required to contribute a minimum of only one day of the period to be included. Subsequently, we will estimate period prevalence with participants required to be observed for the full period for them to be included.

	D2.2.3 – Study Protocol for C1-001	
	Author(s): [name], [name], [name], [name]	Version: 2.0 - Final
	Dissemination level: Public	

[figure not shown]

Figure 3. Point and period prevalence

A summary of the analyses being performed in the study are detailed below in **Table 5**. As mentioned above, these analyses vary based on prevalence type (primary: 5-year partial prevalence, sensitivity: 2-year partial prevalence, and complete prevalence), 2) prevalence estimate (primary: point prevalence, sensitivity: period prevalence), 3) prior history requirement for study population (primary: 365 days, sensitivity: 0 and 1,095 days), 4) observable time requirement for period prevalence (primary: not applicable, sensitivity: one day and full period year).

Table 5. Summary of analysis settings

Analysis	Type	Prevalence estimate	Study population: prior history required before contributing follow up time	Observable time required for time period (period prevalence only)
5-year partial prevalence*				
1	Primary	Point prevalence	365 days	N/A
2	Sensitivity	Period prevalence (annual)	365 days	One day
3	Sensitivity	Period prevalence (annual)	365 days	Full year
4	Sensitivity	Point prevalence	0 days	N/A
5	Sensitivity	Period prevalence (annual)	0 days	One day
6	Sensitivity	Period prevalence (annual)	0 days	Full year
6	Sensitivity	Point prevalence	1095 days	N/A
7	Sensitivity	Period prevalence (annual)	1095 days	One day
8	Sensitivity	Period prevalence (annual)	1095 days	Full year
2-year partial prevalence†				
9	Sensitivity	Point prevalence	365 days	N/A
10	Sensitivity	Period prevalence (annual)	365 days	One day
11	Sensitivity	Period prevalence (annual)	365 days	Full year
12	Sensitivity	Point prevalence	0 days	N/A
13	Sensitivity	Period prevalence (annual)	0 days	One day
14	Sensitivity	Period prevalence (annual)	0 days	Full year
15	Sensitivity	Point prevalence	1095 days	N/A
16	Sensitivity	Period prevalence (annual)	1095 days	One day
17	Sensitivity	Period prevalence (annual)	1095 days	Full year
Complete prevalence‡				
18	Sensitivity	Point prevalence	365 days	N/A
19	Sensitivity	Period prevalence (annual)	365 days	One day

	D2.2.3 – Study Protocol for C1-001	
	Author(s): [name], [name], [name], [name]	Version: 2.0 - Final
	Dissemination level: Public	

Analysis	Type	Prevalence estimate	Study population: prior history required before contributing follow up time	Observable time required for time period (period prevalence only)
20	Sensitivity	Period prevalence (annual)	365 days	Full year
21	Sensitivity	Point prevalence	0 days	N/A
22	Sensitivity	Period prevalence (annual)	0 days	One day
23	Sensitivity	Period prevalence (annual)	0 days	Full year
24	Sensitivity	Point prevalence	1095 days	N/A
25	Sensitivity	Period prevalence (annual)	1095 days	One day
26	Sensitivity	Period prevalence (annual)	1095 days	Full year

*For 5-year partial prevalence individuals will be considered as a prevalent case if they had their initial diagnosis observed in the prior 1,825 days. *For 2-year partial prevalence will be considered as a prevalent case if they had a relevant record observed in the prior 730 days. †For complete prevalence individuals will be considered as a prevalent case if they have ever had a relevant record previously.

8.9 Evidence synthesis

Results will be presented separately by database.

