3. ABSTRACT

Title

Prevalence of rare blood cancers in Europe

Rationale and Background

Substantial uncertainty surrounds the prevalence of rare blood cancers. Using real-world data, brought together as part of DARWIN EU®, we aim to estimate the prevalence of rare blood cancers in order to see if they still meet the condition to be classified as a rare disease.

Research question and Objectives

Research question

What is the prevalence of rare blood cancers in Europe?

Study objectives

Objective 1: To estimate the prevalence of follicular lymphoma between 1st January 2010 and the end of available data in data sources from across Europe, stratified by age and sex

Objective 2: To estimate the prevalence of diffuse Large B-Cell Lymphoma between 1st January 2010 and the end of available data in data sources from across Europe, stratified by age and sex

Objective 3: To estimate the prevalence of multiple myeloma between 1st January 2010 and the end of available data in data sources from across Europe, stratified by age and sex

Objective 4: To estimate the prevalence of chronic lymphocytic leukaemia between 1st January 2010 and the end of available data in data sources from across Europe, stratified by age and sex

Objective 5: To estimate the prevalence of acute myeloid leukaemia between 1st January 2010 and the end of available data in data sources from across Europe, stratified by age and sex

Objective 6: To estimate the prevalence of acute lymphocytic leukaemia between 1st January 2010 and the end of available data in data sources from across Europe, stratified by age and sex

	D2.2.3 – Study Protocol for C1-001	
	Author(s): [name], [name], [name], [name]	Version: 2.0 - Final
		Dissemination level: Public

Research Methods

Study design

Population-based cohort

Population

All people in a database will be eligible for inclusion in the study. Included study participants will need to have some observation time during the study period and, for the primary analysis, have a year of prior history available. In sensitivity analyses the requirement for prior history will first be removed, and then increased to three years.

Variables

Two age groupings will be used in the study: 1) 0-9; 10-19; 20-29; 30-39; 40-49; 50-59; 60-69; 70-79; 80-89; 90-99; 100+, and 2) 0-44; 45-64; 65 and over. The sex (male/ female) of study participants will also be identified.

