Study outcomes will be identified based on the presence of a relevant diagnosis or observation. For the primary analysis, 5-year partial prevalence will be estimated and so individuals will be considered as a prevalent case if they have had their first diagnosis in the prior 5 years. In sensitivity analyses, 2-year partial prevalence and complete prevalence will be estimated. For the latter, once identified as a case, an individual will remain so until their exit from the study (i.e. considering people diagnosed with malignancies to always be affected by the condition).

Data sources

1. Integrated Primary Care Information Project (IPCI), The Netherlands
2. Sistema d'Informació per al Desenvolupament de la Investigació en Atenció Primària (SIDIAP), Spain
3. The Clinical Practice Research Datalink (CPRD) GOLD database
4. IQVIA LPD Belgium
5. IQVIA DA Germany

Sample size

No sample size has been calculated as this is a Disease Epidemiology Study where we are interested in the prevalence of haematological cancers in as large and representative a denominator population as possible.

Data analyses

In line with EMA guidelines for the estimation of the prevalence of rare disease, point prevalence will be used for the primary analysis. The prevalence of each outcome of interest calculated on an annual basis as of the 1st January for each year, estimated overall and stratified by age and sex. As a sensitivity analysis annual period prevalence will also be estimated. A minimum cell count of 5 will be used when reporting results, with any smaller counts obscured.

	D2.2.3 – Study Protocol for C1-001	
	Author(s): [name], [name], [name], [name]	Version: 2.0 - Final
		Dissemination level: Public

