6. RATIONALE AND BACKGROUND

The Committee for Orphan Medicinal Products (COMP) is the European Medicines Agency's (EMA) committee responsible for recommending orphan designation of medicines for rare diseases. It was established in 2000 when new legislation was introduced to encourage the development of medicinal products for rare diseases. One important criterion for granting an orphan designation to a medicine is a prevalence threshold of maximum 5 in 10,000 for the associated condition at the time of application. Of the submissions to the COMP, around 35% are for oncological conditions and around 42% of designations of orphan medicinal products in oncology granted by the COMP between 2000 and 2015 related to rare haematological malignancies.¹

Prevalence estimates, such as of rare haematological malignancies, are a frequent source of uncertainty when submissions to the COMP are being assessed.² In particular, limited availability of population-based epidemiological studies has often led to the use of indirect methods for calculations of prevalence which often involves various assumptions. In addition, time trends in prevalence may also be present meaning that certain conditions that previously satisfied the prevalence criterion for orphan designation in the past may no longer do so. Indeed, increased prevalence has previously been noted for a number of rare haematological malignancies, which may be explained by improved survival and aging populations.¹ In this study the prevalence of rare blood cancers will be measured in Europe over time.

	D2.2.3 – Study Protocol for C1-001	
	Author(s): [name], [name], [name], [name]	Version: 2.0 - Final
	Dissemination level: Public	

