IQVIA LPD Belgium is a computerised network of GPs who contribute to a centralised database of anonymised data of patients with ambulatory visits. Currently, around 300 GPs from 234 practices are contributing to the database covering 1.1M patients from a total of 11.5M Belgians (10.0%). The database covers time from 2005 through the present. Observation time is defined by the first and last consultation dates.

	D2.2.3 – Study Protocol for C1-001	
	Author(s): [name], [name], [name], [name]	Version: 2.0 - Final
	Dissemination level: Public	

IQVIA Disease Analyser (DA) Germany

IQVIA Disease Analyser (DA) Germany is collected from extracts of patient management software used by GPs and specialists practicing in ambulatory care settings. Data coverage includes more than 34M distinct person records out of a total population of 80M (42.5%) in the country and collected from 2,734 providers. Patient visiting more than one provider are not cross identified for data protection reasons and therefore recorded as separate in the system. Dates of service include from 1992 through present. Observation time is defined by the first and last consultation dates. Germany has no mandatory GP system and patients have free choice of specialist. As a result, data are collected from visits to 28.8% General, 13.4% Orthopaedic Surgery, 11.8% Otolaryngology, 11.2% Dermatology, 7.7% Obstetrics/Gynaecology, 6.2% various Neurology and Psychiatry 7.0% Paediatric, 4.6% Urology, 3.7% Cardiology, 3.5% Gastroenterology, 1.5% Pulmonary and 0.7% Rheumatology practices.

Table 2. Description of the selected Data Sources.

Country	Name of Database	Justification for Inclusion	Health Care setting (e.g. primary care, specialist care, hospital care)	Type of Data (EHR, claims, registries)	Number of active subjects
The Netherlands	Integrated Primary Care Information Project (IPCI)	Database selected for Y1 of Darwin EU® and has information on blood cancers	Primary care	EHR	1.4 million
Spain	Sistema d'Informació per al Desenvolupament de la Investigació en Atenció Primària (SIDIAP)	Database selected for Y1 of Darwin EU® and has information on blood cancers	Primary care with hospital linkage	EHR	5.8 million
United Kingdom	The Clinical Practice Research Datalink (CPRD) GOLD database	Database selected for Y1 of Darwin EU® and has information on blood cancers	Primary care	EHR	3 million

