9. DATA MANAGEMENT

All databases will have been mapped to the OMOP common data model. This enables the use of standardised analytics and tools across the network since the structure of the data and the terminology system is harmonised. The OMOP CDM is developed and maintained by the Observational Health Data Sciences and Informatics (OHDSI) initiative and is described in detail on the wiki page of the CDM: <https://ohdsi.github.io/CommonDataModel> and in The Book of OHDSI: <http://book.ohdsi.org>

This analytic code for this study will be written in R. Each data partner will execute the study code against their database containing patient-level data and will then return the results set which will only contain aggregated data. The results from each of the contributing data sites will then be combined in tables and figures for the study report.

	D2.2.3 – Study Protocol for C1-001	
	Author(s): [name], [name], [name], [name]	Version: 2.0 - Final
		Dissemination level: Public

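### The overall prevalence in each database is crude, and no planned analysis relates it to the age-sex structure of Europe before it is read against 5 in 10,000

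*Protocol*

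**What the plan says.** - **Purpose.** The Abstract says that prevalence is estimated "in order to see if they still meet the condition to be classified as a rare disease". Section 6 gives the criterion as "a prevalence threshold of maximum 5 in 10,000 for the associated condition", applied at the time of application, and names ageing populations as one possible reason for rising prevalence. The research question in section 7 concerns Europe.
- **Estimator.** Section 8.8 defines prevalence as cases divided by the population at risk. Section 8.1 has it "estimated overall and stratified by age and sex". No weights or reference population are named.
- **Analyses.** Table 5 has 27 rows (the number 6 is used twice). They vary the type of prevalence, point or period, prior history and observable time. None is standardised.
- **Synthesis.** Section 8.9: "Results will be presented separately by database".
- **Age bands.** Section 8.6.3 plans 10-year bands, with 0-44, 45-64 and 65 and over as the fallback where counts are low. It does not say whether age is crossed with sex.
- **Output.** Section 9 says that each partner "will then return the results set which will only contain aggregated data". The Abstract adds: "A minimum cell count of 5 will be used when reporting results, with any smaller counts obscured".

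**The concern.** A crude overall proportion is a weighted mean of age-sex-specific prevalences, and the weights are the database's own age-sex mix. The protocol gives no age-sex distribution for any database, but section 8.2 gives reasons not to assume that each one mirrors Europe:

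- The German data come from a mix of practice types, among them "7.7% Obstetrics/Gynaecology, 6.2% various Neurology and Psychiatry 7.0% Paediatric".
- CPRD GOLD practices are 52% Scottish and 28% Welsh.
- In Belgium and Germany, observation time runs from first to last consultation. With the one-year history rule, the denominator is people who consult repeatedly, not residents.

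Two databases with the same age-specific prevalence could then fall on opposite sides of the limit. Differences between databases, and the trend from 2010, would mix disease frequency with age structure. The limitations in section 11 do not mention this.

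**Working it through.** The protocol states no figure to reproduce. All rates, age mixes and reference weights below are assumptions. Database sizes are the active subjects in Table 2.

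**1. Effect of age mix.** Crude prevalence = sum of (age share × age-specific prevalence). Assume 0.1, 4 and 18 per 10,000 at ages 0-44, 45-64 and 65+, with 27% aged 45-64 and a share *s* aged 65+:

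0.1 × (0.73 − *s*) + 4 × 0.27 + 18 × *s* = 1.153 + 17.9 × *s*

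| Share 65+ | 15% | 18% | 20% | 22% | 25% |
|---|---|---|---|---|---|
| Crude per 10,000 | 3.8 | 4.4 | 4.7 | 5.1 | 5.6 |

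The limit is crossed at *s* = (5 − 1.153)/17.9 = 21.5%.

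**2. Other age profiles.** The age mixes (0-44 / 45-64 / 65+) are 58/26/16%, 52/27/21% and 47/28/25%.

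| Assumed rates per 10,000 | 16% aged 65+ | 21% | 25% | Crosses 5? |
|---|---|---|---|---|
| 0.2 / 4 / 18 | 4.04 | 4.96 | 5.71 | yes |
| 0.5 / 5 / 13 | 3.7 | 4.3 | 4.9 | no |
| 0.6 / 0.4 / 0.5 | 0.53 | 0.53 | 0.52 | no |

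For example, 0.2 × 0.58 + 4 × 0.26 + 18 × 0.16 = 4.04.

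**3. Standardising later from the reported cells.** Directly standardised prevalence = sum of (reference weight × cases/denominator). An obscured cell holds 0 to 4 cases. With reference weights close to the database's mix, the bounds are at most about 4 × (obscured cells)/N apart.

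- Belgium, N = 435,200, 10 cells obscured: 40/435,200 = 0.92 per 10,000.
- IPCI, N = 1.4 million, 10 cells: 0.29. SIDIAP, N = 5.8 million, 10 cells: 0.07.
- Belgium, broad bands by sex, 2 of 6 cells obscured: 8/435,200 = 0.18.

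A worked case uses 10-year bands by sex. From 0-9 to 100+:

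- assumed rates per 10,000: 0.02, 0.03, 0.05, 0.2, 1, 4, 10, 18, 20, 15, 10 (× 1.25 in men, × 0.8 in women)
- database shares (%): 11, 11.5, 12.5, 13, 13, 14, 11.5, 8, 4.5, 0.98, 0.02
- reference shares (%): 9.5, 10.5, 11, 12.5, 14, 14.5, 12.5, 9.5, 5, 0.98, 0.02

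| Database | Crude | Standardised | Bounds from cells alone | Cells below 5 |
|---|---|---|---|---|
| Belgium | 4.46 | 4.97 | 4.64 to 5.87 | 14 of 22 |
| IPCI | 4.46 | 4.97 | 4.94 to 5.21 | 10 of 22 |
| SIDIAP | 4.47 | 4.98 | 4.97 to 5.02 | 8 of 22 |

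The Belgian bounds tighten if the overall count is also shown. In this example there are 194 cases, 180 of them in visible cells, so 14 in the obscured ones. Each obscured case adds (reference share/database share) × 10,000/435,200. The ratio lies between 9.5/11 = 0.864 and 14/13 = 1.077, so each case adds 0.0198 to 0.0247. The result is 4.64 + 14 × 0.0198 = 4.91 to 4.64 + 14 × 0.0247 = 4.98. This needs fully crossed age-by-sex cells, which the protocol does not promise.

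**4. Choice of reference.** Take the rates in step 1 and let Europe's share aged 65+ really rise from 18% to 22%. Prevalence then rises from 4.4 to 5.1. A reference fixed at 18% would show 4.4 at both dates and hide the crossing.

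**The case against.** The strongest objection is that a crude proportion in a nationally representative source is that country's prevalence, and section 8.2 calls the IPCI practices representative of the Netherlands. Since section 6 treats ageing as a reason why a condition may cease to qualify, ageing belongs to the answer and should not be adjusted away. This stands. It is why the crude figures and crude trend must stay, and why a single fixed reference must not be used to read against the limit. It does not link five national or regional figures to Europe.

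A reader might also infer that the output cannot be standardised afterwards. The documents do not support that. Obscuring is stated for reporting, not for data leaving the sites. Age and sex strata are planned, and obscured cells can be bounded. Nor does it matter that cuts at 45 and 65 do not nest in the 10-year bands: the broad bands can be standardised on their own, although age differences within 65 and over remain.

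Two further points stand. The crossing depends on assumed rates, and practice location or specialty does not establish the direction of any age difference.

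A statistical analysis plan that is not shown may name a reference population. But the protocol itself fixes the estimator, the list of analyses and the synthesis rule. Sites run common code and return aggregates, so the output has to be specified before they run it.

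**Conclusion.** The point holds as a low-cost improvement, not as an error that invalidates the study. The overall figures are crude by definition, and nothing in Table 5 or section 8.9 relates them to Europe's age-sex structure. With assumed age-steep rates, a change from 15% to 25% aged 65 and over moves the crude figure by 1.8 per 10,000 (3.8 to 5.6), across the limit. With a flatter profile the figure moves but does not cross, and for a low-rate flat profile it hardly changes.

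Standardising later is feasible and tight in the larger databases. In Belgium with 10-year bands it is imprecise from the cells alone (4.64 to 5.87 in the example). It becomes tight only if the overall count and crossed age-by-sex cells are available. Computing the value at the sites removes this dependence.

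**What to change.** In sections 8.8 and 8.9, for analysis 1 and for complete point prevalence with 365 days of history (analysis 18):

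- Have the common code compute at each site, before small counts are obscured, overall prevalence directly standardised by age band and sex. Report it with its interval beside the crude value for each 1 January.
- For reading against 5 in 10,000, use the European population of the same calendar year as the reference, so that real ageing is kept.
- Use one fixed European reference only to compare databases and to separate age structure from other change in the trend. Keep the crude trend.
- Name both references, and state that age is crossed with sex.

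The cost is about a paragraph of text and a few lines of code, with no new data. Section 5 still lists code creation and execution as to be confirmed. The downside is a second set of overall figures with slightly wider intervals. Standardisation does not repair under-recording, or the separate records that section 8.2 describes for German patients who see more than one provider.
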